## Central Laboratory Assessments

The following samples will be sent to one or several Sponsor-designated central laboratories or to the Sponsor for analysis:

- Serum samples for obinutuzumab PK analysis using a validated assay
- *Serum samples for rituximab PK analysis using a validated assay*
- Serum and plasma samples for polatuzumab vedotin PK analysis using a validated assay
- Plasma samples for lenalidomide PK analysis using a validated assay
- Serum samples for assessment of obinutuzumab HAHAs using a validated assay
- *Serum samples for assessment of rituximab HACAs using a validated assay*
- Serum samples for assessment of polatuzumab vedotin ATAs using a validated assay
- Tumor tissue samples (obtained within 6 months prior to the initiation of study treatment for DLBCL or within 12 months prior to the initiation of study treatment for FL) and the corresponding pathology report for retrospective central confirmation of the diagnosis of FL or DLBCL and for exploratory research on candidate biomarkers (see [Table 14](#))

The specimen must contain adequate evaluable tumor cells ( $\geq 20\%$  for excisional biopsy and  $\geq 50\%$  for core biopsy).

Formalin-fixed paraffin-embedded tissue blocks are preferred over slides. Tissue blocks that are not formalin fixed will be accepted in countries that use a fixative other than paraformaldehyde, but information on the type of fixative should be included. If a tissue block is not available, a minimum of 20 serial, freshly cut, unstained slides accompanied by a tumor block punch may be sent. A tumor block or tumor block punch is required for construction of a tissue microarray.

If archival tissue is unavailable or unacceptable according to above criteria, a pretreatment core-needle, excisional, or incisional tumor biopsy is required. Cytological or fine-needle aspiration samples are not acceptable.

If the available biopsy was performed more than 12 months prior to Day 1 of Cycle 1, or the patient received anti-lymphoma treatment between the time of the most recent available biopsy and Day 1 of Cycle 1, a core-needle biopsy is strongly recommended.

The sample should be shipped according to instructions provided in the laboratory manual. The remainder of the archival tissue blocks will be returned to the local pathology laboratory, according to country-specific procedures after the clinical study report has been published or upon request.

- Tumor biopsy samples obtained at the time of progression (unless no adequate tumor site is accessible) for exploratory research on candidate biomarkers (see [Table 14](#))
- Plasma samples for exploratory research on candidate biomarkers (see [Table 14](#))

- Whole blood samples for exploratory research on candidate biomarkers (see [Table 14](#))
- Whole blood for lymphocyte immunophenotyping (see [Table 14](#))

Exploratory biomarker research may include, but will not be limited to, the biomarkers listed in [Table 14](#).

**Table 14 Proposed Non-Inherited Biomarkers**

Sample Type	Timing	Proposed Non-Inherited Biomarkers
Archival or fresh pretreatment and progression tumor tissue	Prior to study (archival) or baseline (fresh) and at disease progression	
 
• For DLBCL patients only: DLBCL cell-of-origin subtype (ABC vs. GCB), BCL2, MYC
 
• For both DLBCL and FL patients: target expression BCL2 and CD79b, immune infiltrate, cereblon (and surrogates)
 
• Lymphoma-related genetic changes (DNA) and gene expression (mRNA) or protein expression (IHC associated with response or potential resistance)
 
• Lymphoma index clone in MRD
 

Plasma isolated from whole blood	Baseline and subsequent timepoints during treatment (patients who enroll in the expansion phase only)	
 
• Circulating lymphoma cells and/or cell-free circulating tumor DNA (detection of minimal residual disease)
 

Whole blood	Baseline and subsequent timepoints during and after treatment	
 
• Lymphocyte immunophenotyping, including B-cell counts (CD19), T-cell counts (CD3, CD4, and CD8), and NK-cell counts (CD16 and CD56)
 

Plasma	Baseline (predose and postdose) and subsequent timepoints (predose) during treatment	
 
• Cytokines characteristic of T-cell activation and lenalidomide activity (e.g., IL-8 and IFN<math>\gamma</math>)
 

ABC=activated B cell-like; DLBCL=diffuse large B-cell lymphoma; FL=follicular lymphoma; GCB=germinal-center B cell-like; IFN $\gamma$ =interferon  $\gamma$ ; IHC = immunohistochemistry; IL-8=interleukin 8; NK-cell=natural killer cell.

Note: Exploratory biomarker research may include, but will not be limited to, the biomarkers listed in this table.

Samples collected for PK and immunogenicity analyses may be used for assay development purposes and additional safety and immunogenicity assessments, as appropriate.

*Unless the patient gives specific consent for his or her leftover samples to be stored for optional exploratory research, biological samples will be destroyed when the final Clinical Study Report has been completed, with the following exception(s):*

- *Serum [or plasma] samples collected for PK and immunogenicity (ATA) analysis may be needed for additional PK and ATA assay development and validation, and additional immunogenicity characterization; therefore, these samples will be destroyed no later than 5 years after the final Clinical Study Report has been completed (see Section 4.5.8).*

#### **4.5.7 Electrocardiograms**

Single, resting, 12-lead ECG recordings will be obtained at specified timepoints, as outlined in the schedules of assessments (see [Appendix 1](#) and [Appendix 2](#)) and may be obtained at unscheduled timepoints as clinically indicated. ECGs for each patient should be obtained using the same machine wherever possible. Interpretation of the ECG should be performed by the investigator.

#### **4.5.8 Samples for Roche Clinical Repository**

##### **4.5.8.1 Overview of the Roche Clinical Repository**

The Roche Clinical Repository (RCR) is a centrally administered group of facilities used for the long-term storage of human biologic specimens, including body fluids, solid tissues, and derivatives thereof (e.g., DNA, RNA, proteins, peptides). The collection and analysis of RCR specimens will facilitate the rational design of new pharmaceutical agents and the development of diagnostic tests, which may allow for individualized drug therapy for patients in the future.

Specimens for the RCR will be collected from patients who give specific consent to participate in this optional research. RCR specimens will be used to achieve the following objectives:

- To study the association of biomarkers with efficacy, adverse events, or disease progression
- To increase knowledge and understanding of disease biology
- To study drug response, including drug effects and the processes of drug absorption and disposition
- To develop biomarker or diagnostic assays and establish the performance characteristics of these assays

##### **4.5.8.2 Approval by the Institutional Review Board or Ethics Committee**

Collection and submission of biological samples to the RCR is contingent upon the review and approval of the exploratory research and the RCR portion of the Informed Consent Form by each site's Institutional Review Board (IRB) or Ethics Committee (EC) and, if applicable, an appropriate regulatory body. If a site has not been granted

approval for RCR sampling, this section of the protocol (Section 4.5.8) will not be applicable at that site.

#### **4.5.8.3 Sample Collection**

The following samples and derivatives thereof (e.g., DNA, RNA, proteins, peptides) will be collected for research purposes, including, but not limited to, research on dynamic (non-inherited) and genetic (inherited) biomarkers related to obinutuzumab, *rituximab*, polatuzumab vedotin, lenalidomide, B-cell lymphoma, or other types of cancer:

- Peripheral blood (i.e., whole blood)
- Remaining tumor tissue from lymph node biopsy (archival and/or fresh biopsy)
- Remaining peripheral blood (e.g., whole blood, plasma, and serum)

For sampling procedures, storage conditions, and shipment instructions, see the laboratory manual.

RCR specimens will be destroyed no later than 15 years after the date of final closure of the associated clinical database. The RCR storage period will be in accordance with the IRB/EC-approved Informed Consent Form and applicable laws (e.g., health authority requirements).

#### **4.5.8.4 Confidentiality Confidentiality for All RCR Specimens**

Specimens and associated data will be labeled with a unique patient identification number.

Patient medical information associated with RCR specimens is confidential and may be disclosed to third parties only as permitted by the Informed Consent Form (or separate authorization for use and disclosure of personal health information) signed by the patient, unless permitted or required by law.

Data generated from RCR specimens must be available for inspection upon request by representatives of national and local health authorities and Roche monitors, representatives, and collaborators, as appropriate.

Data derived from RCR specimen analysis on individual patients will generally not be provided to study investigators unless a request for research use is granted. The aggregate results of any research conducted using RCR specimens will be available in accordance with the effective Roche policy on study data publication.

Any inventions and resulting patents, improvements, and/or know-how originating from the use of the RCR data will become and remain the exclusive and unburdened property of Roche, except where agreed otherwise.

## **Additional Confidentiality for Specimens Used for Genetic Research**

Given the sensitive nature of genetic data, Roche has implemented additional processes to ensure patient confidentiality for RCR specimens collected for genetic research. Upon receipt by the RCR, specimens for genetic research are “double-coded” by replacing the patient identification number with a new independent number. Data generated from the use of these specimens and all clinical data transferred from the clinical database and considered relevant are also labeled with this same independent number. A “linking key” between the patient identification number and this new independent number is stored in a secure database system. Access to the linking key is restricted to authorized individuals and is monitored by audit trail. Legitimate operational reasons for accessing the linking key are documented in a standard operating procedure. Access to the linking key for any other reason requires written approval from the Pharma Repository Governance Committee and Roche’s Legal Department, as applicable.

### **4.5.8.5 Consent to Participate in the Roche Clinical Repository**

The Informed Consent Form will contain a separate section that addresses participation in the RCR. The investigator or authorized designee will explain to each patient the objectives, methods, and potential hazards of participation in the RCR. Patients will be told that they are free to refuse to participate and may withdraw their specimens at any time and for any reason during the storage period. A separate, specific signature will be required to document a patient’s agreement to provide optional RCR specimens. Patients who decline to participate will not provide a separate signature.

The investigator should document whether or not the patient has given consent to participate by completing the RCR Research Sample Informed Consent eCRF.

In the event of an RCR participant’s death or loss of competence, the participant’s specimens and data will continue to be used as part of the RCR research.

### **4.5.8.6 Withdrawal from the Roche Clinical Repository**

Patients who give consent to provide RCR specimens have the right to withdraw their specimens from the RCR at any time for any reason. If a patient wishes to withdraw consent to the testing of his or her specimens, the investigator must inform the Medical Monitor in writing of the patient’s wishes through use of the RCR Subject Withdrawal Form and, if the trial is ongoing, must enter the date of withdrawal on the RCR Research Sample Withdrawal of Informed Consent eCRF. The patient will be provided with instructions on how to withdraw consent after the trial is closed. A patient’s withdrawal from Study GO29834 does not, by itself, constitute withdrawal of specimens from the RCR. Likewise, a patient’s withdrawal from the RCR does not constitute withdrawal from Study GO29834.

### **4.5.8.7 Monitoring and Oversight**

RCR specimens will be tracked in a manner consistent with Good Clinical Practice (GCP) by a quality-controlled, auditable, and appropriately validated laboratory information

management system, to ensure compliance with data confidentiality as well as adherence to authorized use of specimens as specified in this protocol and in the Informed Consent Form. Roche monitors and auditors will have direct access to appropriate parts of records relating to patient participation in the RCR for the purposes of verifying the data provided to Roche. The site will permit monitoring, audits, IRB/EC review, and health authority inspections by providing direct access to source data and documents related to the RCR samples.

## **4.6 PATIENT, TREATMENT, STUDY, AND SITE DISCONTINUATION**

### **4.6.1 Patient Discontinuation**

Patients have the right to voluntarily withdraw from the study at any time for any reason. In addition, the investigator has the right to withdraw a patient from the study at any time. Reasons for withdrawal from the study may include, but are not limited to, the following:

- Patient withdrawal of consent at any time
- Any medical condition that the investigator or Sponsor determines may jeopardize the patient's safety if he or she continues in the study
- Investigator or Sponsor determines that it is in the best interest of the patient
- Patient non-compliance (e.g., consistent failure to show up for scheduled visits)

Every effort should be made to obtain information on patients who withdraw from the study. The primary reason for withdrawal from the study should be documented on the appropriate eCRF. However, patients will not be followed for any reason after consent has been withdrawn.

If a patient withdraws consent, this request must be documented in the source documents and signed by the investigator. Study personnel may use a public information source (e.g., county records) to obtain information about survival status.

### **4.6.2 Study Treatment Discontinuation**

Study treatment should be permanently discontinued in patients who experience any of the following:

- Anaphylaxis, acute respiratory distress, or Grade 4 IRR  
If a Grade 3 IRR is recurrent during the second or subsequent cycles, study treatment may be discontinued at the discretion of the investigator, following an individual benefit-risk assessment.
- Any adverse event that meets criteria for permanent discontinuation per guidelines provided in Section 5.1
- Pregnancy
- Disease progression

The primary reason for study treatment discontinuation should be documented on the appropriate eCRF.

Patients who discontinue study treatment will not be replaced, except as outlined below:

- During the dose-escalation phase, patients who discontinue study treatment prior to completing the DLT assessment window for reasons other than a DLT will be replaced by an additional patient at that same dose level.
- Patients who discontinue prior to receiving at least one dose of each component of the combination will be replaced.

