## 2. **OBJECTIVES AND ENDPOINTS**

This study will evaluate the safety, efficacy, and pharmacokinetics of induction treatment consisting of obinutuzumab in combination with polatuzumab vedotin and lenalidomide (G+Pola+Len) in patients with R/R FL *and rituximab in combination with polatuzumab vedotin and lenalidomide (R+Pola+Len) in patients with R/R DLBCL*, followed by post-induction treatment with G+Len (*referred to as maintenance*) in patients with FL who achieve a CR, PR, or stable disease at EOI and *post-induction treatment with rituximab plus lenalidomide (R+Len; referred to as consolidation)* in patients with DLBCL who achieve a CR or PR at EOI. Specific objectives and corresponding endpoints for the study are outlined below.

In this study, "study treatment" refers to the protocol-mandated treatments under study (i.e., obinutuzumab, *rituximab*, polatuzumab vedotin, and lenalidomide).

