**Figure 5 Guidelines for Obinutuzumab Infusions: First Infusion**

[figure not shown]

IRR = infusion-related reaction.

a All patients should receive full premedication with an oral corticosteroid, antihistamine, and oral analgesic/antipyretic prior to the first obinutuzumab infusion. Refer to Section 4.3.2.5 for details.

b Supportive treatment should include acetaminophen/paracetamol and an antihistamine such as diphenhydramine, if not administered within the previous 4 hours. Intravenous saline may be indicated. For bronchospasm, urticaria, or dyspnea, patients may require antihistamines, oxygen, corticosteroids (e.g., 100 mg oral prednisone or equivalent), and/or bronchodilators. For anaphylaxis precautions, see Appendix 8.

**Figure 6** *Guidelines for Obinutuzumab Infusions: Second and Subsequent Infusions*

IRR =infusion-related reaction; q30 =every 30.

a Patients should receive full premedication with an oral corticosteroid, antihistamine, and oral analgesic/antipyretic prior to the obinutuzumab infusion. In the case of a recurrent Grade 3 IRR, obinutuzumab may be discontinued at the discretion of the investigator, following an individual benefit–risk assessment.

b Patients who experience wheezing, urticaria, or other symptoms of anaphylaxis must receive full premedication prior to all subsequent doses.

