**Table 12 Administration of First and Subsequent Infusions of Rituximab**

First Infusion (Day 1 of Cycle 1)	Subsequent Infusions

 
• Begin infusion at an initial rate of 50 mg/hr.
 
• If no infusion-related or hypersensitivity reaction occurs, increase the infusion rate in 50-mg/hr increments every 30 minutes to a maximum of 400 mg/hr.
 
• If a reaction develops, stop or slow the infusion. Administer medications and supportive care in accordance with institutional guidelines. If the reaction has resolved, resume the infusion at a 50% reduction in rate (i.e., 50% of rate being used at the time when the reaction occurred).
 
	
 
• If the patient experienced an infusion-related or hypersensitivity reaction during the prior infusion, use full premedication, including 100 mg of prednisone/prednisolone or 80 mg of methylprednisolone or equivalent (until no further IRR occurs); begin infusion at an initial rate of 50 mg/hr; and follow instructions for first infusion.
 
• If the patient tolerated the prior infusion well (defined by an absence of Grade 2 reactions during a final infusion rate of <math>\geq</math> 100 mg/hr), begin infusion at a rate of 100 mg/hr.
 
• If no reaction occurs, increase the infusion rate in 100-mg/hr increments every 30 minutes to a maximum of 400 mg/hr.
 
• If a reaction develops, stop or slow the infusion. Administer medications and supportive care in accordance with institutional guidelines. If the reaction has resolved, resume the infusion at a 50% reduction in rate (i.e., 50% of rate being used at the time when the reaction occurred).
 

No dose modification for rituximab is allowed. Guidelines for treatment delays or discontinuation are provided in Section 5.1.6.

Premedication with a corticosteroid, analgesic/antipyretic, and antihistamine, as outlined in Section 4.3.2.5, is required to reduce the incidence and severity of IRRs. For anaphylaxis precautions, see Appendix 8.

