**Table 13 Premedication**

Timepoint	Patients Requiring Premedication	Premedication	Administration
Cycle 1, Day 1	
 
All patients
 
	
 
Oral corticosteroida
 
	Complete ≥ 1 hour prior to obinutuzumab or rituximab infusion
	
 
All patients
 
	
 
Antihistamine drugb
 
Oral analgesic/antipyreticc
 
	Administer ≥ 30 minutes prior to obinutuzumab or rituximab infusion
	
 
Patients at risk for TLS (e.g., because of bulky disease or renal impairment [creatinine clearance < 70 mL/min])
 
	
 
Allopurinol or suitable alternative, such as rasburicase, along with adequate hydration
 
	Administer prior to obinutuzumab or rituximab infusion
Cycle 1, Days 8 and 15  Cycles 2 and Beyond, Day 1	
 
Patients with no IRR during the previous infusion
 
	
 
Oral analgesic/anti-pyreticc
 
	Administer at least 30 minutes prior to obinutuzumab infusion. For patients receiving rituximab, premedication may be omitted at the investigator's discretion.
	
 
Patients with Grade 1 or 2 IRR during the previous infusion
 
	
 
Antihistamine drugb
 
Oral analgesic/antipyreticc
 
	Administer ≥ 30 minutes prior to obinutuzumab or rituximab infusion
	
 
Patients with Grade 3 IRR, wheezing, urticarial, or other symptoms of anaphylaxis during the previous infusion
 
Patients with bulky disease
 
	
 
Oral corticosteroida
 
	Complete ≥ 1 hour prior to obinutuzumab or rituximab infusion
			
 
Antihistamine drugb
 
Oral analgesic/antipyreticc
 

	
 
Patients still at risk for TLS
 
	
 
Allopurinol or suitable alternative, such as rasburicase, along with adequate hydration
 
	Administer prior to obinutuzumab or rituximab infusion

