#### **5.1.1.1 Infusion-Related Reactions**

IRRs have been reported predominantly during the first infusion of obinutuzumab. The incidence and severity of IRRs decreased substantially with the second and subsequent infusions. In the majority of patients, IRRs were mild or moderate and resolved with the slowing or interruption of the infusion and supportive care. The commonly experienced IRRs have been characterized by hypotension, fever, chills, flushing, nausea, vomiting, hypertension, fatigue, and other symptoms.

IRRs may be clinically indistinguishable from IgE-mediated allergic or anaphylactic reactions; anaphylaxis has been reported in patients treated with obinutuzumab.

Hypotension may occur during obinutuzumab IV infusions. Therefore, withholding of antihypertensive treatments should be considered for 12 hours prior to and throughout each obinutuzumab infusion and for the first hour after administration. Patients at acute risk of hypertensive crisis should be evaluated for the benefits and risks of withholding their antihypertensive medication.

Patients who have preexisting cardiac or pulmonary conditions should be monitored carefully throughout the infusion and the post-infusion period.

Guidelines for medical management of IRRs and anaphylaxis are provided in Section 4.3.2.1 and Appendix 8.

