**Table 19 Guidelines for Management of Non-Hematologic Toxicities During Induction**

Event		Action to Be Taken
General guidance for treatment delays and discontinuation		
 
– If study treatment is withheld for >21 days because of a toxicity that is attributable to study treatment, permanently discontinue study treatment.
 
– When a treatment cycle is delayed because of toxicity resulting from any component of the regimen, all study treatment should be held and resumed together to remain synchronized.
 
– If one drug is discontinued, treatment with the other two drugs may be continued for patients experiencing clinical benefit as determined by the investigator after discussion with the Medical Monitor.
 

IRRs and anaphylaxis		
 
– Guidelines for the management of IRRs are provided in Section 4.3.2.1 for obinutuzumab, Section 4.3.2.2 for rituximab, and Section 4.3.2.3 for polatuzumab vedotin.
 
– In case of anaphylaxis, study treatment should be permanently discontinued.
 

Renal toxicity		
 
– Adjust the dose of lenalidomidea as outlined below: 
 
• If creatinine clearance is <math>\geq 30</math> but <math>< 50</math> mL/min, lenalidomide should be given at a dose of 10 mg/day.
 
• If creatinine clearance is <math>< 30</math> mL/min and dialysis is not required, lenalidomide should be given at a dose of 10 mg every other day.
 
• If creatinine clearance is <math>< 30</math> mL/min and dialysis is required, lenalidomide should be given at a dose of 5 mg/day. On dialysis days, the dose should be administered after dialysis.
 
 
 

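### Table 12 restarts and repeats rituximab after any resolved reaction, while Section 4.6.2 and Table 19 end study treatment for anaphylaxis, and the pointer that should link them leads to the wrong section

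*Combined protocol and SAP*

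**What the plan says.** **Provisions that stop treatment.** Section 4.6.2 opens with "Study treatment should be permanently discontinued in patients who experience any of the following", and its first entry is "Anaphylaxis, acute respiratory distress, or Grade 4 IRR". Within that entry, only a recurrent Grade 3 infusion-related reaction (IRR) is left to the investigator's discretion. Table 19, in its row on IRRs and anaphylaxis, says "In case of anaphylaxis, study treatment should be permanently discontinued". Section 2 defines study treatment as the term that "refers to the protocol-mandated treatments under study", so the stop covers every drug in the regimen.

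**Provisions that continue treatment.**
- Table 12 (rituximab), on a reaction during an infusion: stop or slow the infusion, treat, and then "If the reaction has resolved, resume the infusion at a 50% reduction in rate". On the next infusion after an infusion-related or hypersensitivity reaction: full premedication and a restart at the initial rate.
- Table 13 (both antibodies) sets corticosteroid, antihistamine and analgesic cover before the next infusion for "Patients with Grade 3 IRR, wheezing, urticarial, or other symptoms of anaphylaxis during the previous infusion".
- Figure 6 footnote b (obinutuzumab): "Patients who experience wheezing, urticaria, or other symptoms of anaphylaxis must receive full premedication prior to all subsequent doses".

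**Telling the categories apart.** Section 5.1.1.1, on obinutuzumab, says "IRRs may be clinically indistinguishable from IgE-mediated allergic or anaphylactic reactions". Section 5.1.2.1, on rituximab, describes the manifestations as similar, but adds that true hypersensitivity typically starts within minutes of the infusion.

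**The concern.** A site managing a rituximab reaction works from Table 12. Taken literally, it restarts the drug in a patient whom Section 4.6.2 takes off all study treatment. What is at stake is first the safety of that patient, and then consistency: two sites following different pages of the same protocol would treat the same event in opposite ways.

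There is a smaller analytical side. Whether an event is recorded as anaphylaxis or as an IRR can decide whether it counts as a DLT. Whether treatment stops on Day 1 can decide whether the patient is replaced.

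**Working it through.** The point is mainly a comparison of text. The plan states no figure for it.

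**1. The rituximab provisions side by side**

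| Reaction, once resolved | 4.6.2 | Table 19, IRR and anaphylaxis row | Table 12 |
|---|---|---|---|
| Anaphylaxis | Permanent stop | Permanent stop | Resume at half rate; later doses with full premedication |
| Grade 4 IRR | Permanent stop | Not named; refers to the infusion sections | Same, no grade limit |
| Acute respiratory distress | Permanent stop | Not named | Same, if part of a reaction to the infusion |

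Table 12 contains no exception, so the first two rows cannot both be followed.

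**2. Do the cross-references resolve it?** The text under Table 12, in Section 4.3.2.2, points to Section 5.1.6 for delays and discontinuation. That section is on drug-drug interactions. The matching obinutuzumab text in 4.3.2.1 points to 5.1.7, which holds Table 19. Table 19 in turn sends sites back to 4.3.2.2 for rituximab IRRs, and so to Table 12. Appendix 8 tells the site to stop the infusion, treat and observe. It says nothing on permanent discontinuation.

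**3. Table 13 and Figure 6 footnote b.** Both assume a further dose after symptoms of anaphylaxis. Neither says what separates those symptoms from the anaphylaxis in 4.6.2. This is an undefined boundary, not a literal contradiction.

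**4. DLT counting and replacement.** Section 3.1.2.1.1, which also serves the DLBCL escalation, counts related Grade 3 or 4 non-hematologic events in Cycle 1 as DLTs and exempts Grade 3 or 4 IRRs. Anaphylaxis is not among the exemptions.
- A related Grade 3 or 4 event recorded as anaphylaxis would count as a DLT. In a 3+3 cohort it turns 0 of 3 into 1 of 3, which expands the cohort to 6.
- Recorded as a Grade 4 IRR, it is exempt. The patient stops for a reason other than a DLT and is replaced.
- The dosing order is lenalidomide, antibody, polatuzumab vedotin (4.3.2). A stop during the first antibody infusion means that not every component was given, so 4.6.2 replaces the patient. Section 6.2 keeps that patient in the efficacy population, because one dose of any component is enough.

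**5. Can an effect on the CR rate be derived?** The exact 90% lower limit is the 0.05 quantile of Beta(x, n − x + 1). For 28/40 it is 0.560, with an upper limit of 0.817. This reproduces the Table 22 row for 0.70 (0.56, 0.82). Suppose 28/40 is the result when one such patient continues treatment. If the patient is instead stopped on Day 1, scored as a non-responder and replaced, the denominator becomes 41:
- the patient would have responded, and so does the replacement: 28/41, lower limit 0.544;
- the patient would not have responded, but the replacement does: 29/41, lower limit 0.569.

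The limit can move either way. The direction depends on outcomes that the documents cannot supply.

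**The case against.** The best defence is that the stop rules are mandatory and agree on anaphylaxis, while Tables 12 and 13 only set rates and premedication for patients who are to be infused again. On that view the Section 5.1.6 reference is an evident slip, and Appendix 8 already stops the infusion. Table 13 supports this in part: its highest tier names Grade 3 and omits Grade 4, in line with 4.6.2. A reader may also keep anaphylaxis for the diagnosis and treat wheezing or urticaria as lesser features; a Figure 5 footnote lists bronchospasm and urticaria under supportive treatment.

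This stands for Table 13 and Figure 6, where the fault is only a missing definition. The flow charts of Figures 5 and 6 were not legible in the copy reviewed and may hold a stop instruction for obinutuzumab. It does not stand for Table 12, which positively instructs the site to resume, and I found no statement that 4.6.2 takes precedence.

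A reader might infer four stronger things, which the documents do not support:
- **That the patient's participation ends on Day 1.** Section 4.6.2 ends treatment; Section 3.1.6 continues follow-up.
- **That a stopped patient is always non-evaluable for DLT.** Related Grade 3 or 4 anaphylaxis could itself be a DLT.
- **That Section 5.1.1.1 makes the reactions indistinguishable for rituximab too.** It concerns obinutuzumab; Section 5.1.2.1 gives a timing feature for rituximab.
- **That the conflict lowers the CR rate by a known amount.** The replaced patient stays in the denominator, the sign is not fixed, and Section 6.6.1 plans estimation, with no success rule tied to the 55% bound.

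**Conclusion.** The conflict over rituximab is in the current text and holds. Table 12 and Section 4.6.2 give opposite instructions for anaphylaxis and Grade 4 IRR, and the reference that should connect them is wrong. For Table 13 and Figure 6 footnote b, the conclusion is limited to an undefined boundary.

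The main consequence is patient safety and uneven handling between sites. Effects on DLT counting and replacement are possible for individual patients.

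The size cannot be given. Section 1.2.2.2 reports IRRs in 70%–78% with obinutuzumab plus CHOP or bendamustine. Section 3.3.2.4 reports 3 of 19 with obinutuzumab plus lenalidomide, none above Grade 2. Section 5.1.2.1 puts serious rituximab IRRs below 1 in 100. None states how many reactions involve anaphylaxis. The finding rests on Table 12 being read as printed and on no overriding rule elsewhere in the readable text.

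**What to change.** Reconcile Section 4.6.2, Table 19, Table 12, Table 13 and Figure 6 footnote b to a single rule that states which reactions end study treatment and which allow further dosing. The sponsor's medical team makes the clinical choice; this review does not propose one. Tables 12 and 13 and the footnote should then refer to that rule, and the boundary between symptoms of anaphylaxis and anaphylaxis should be defined where the rule is stated. Correct the reference under Table 12 from Section 5.1.6 to 5.1.7.

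The cost is amendment wording in five places and one cross-reference. No visit, test or procedure is added.
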